1. VERSION HISTORY

Table 1. Summary of Changes			
Version/ Date	Associated Protocol Amendment	Rationale	Specific Changes
9 08 Apr 2024	Amendment 15 28-Dec-2023	To clarify the timing of primary analysis based on protocol	Section 5 Added text “The primary analysis will occur after at least 90 FAS participants complete Day 360 (Visit 19) or discontinued from the study prior to Week 52 if they had received Year 1 IP at least one year prior to the data cutoff.”
		Due to the transfer of the viral vector shedding assay to an internal lab during the course of the study and some differences in the results between the 2 assays, the analysis for endpoint viral vector levels are removed from the planned analysis as they may include data from both assays. switch of labs for the	Sections 6.3.8, Appendix 1 Removed analysis for viral vector levels endpoint
		To clarify the FAS definition for PCD analysis and align with protocol	Section 4 Changed the name of Full Analysis Set (FAS) to Full Analysis Set (FAS) (through Week 52) Added footnote to clarify the FAS for PCD analysis
		To evaluate the treatment effect more comprehensively using multiple endpoint	Sections 5.2.4, 6.4 Added global statistical test analysis for specified multiple functional endpoints
		To better present the analysis results	Sections 6.1.1, 6.2.2, 6.2.3, 6.2.4, 6.2.5, Appendix 1 Removed model-based summary of LS means at Week 52 for each age. Added standard error of each LS mean and estimated difference in LS mean in the summary Removed graph for Mean (SD) change from Baseline at Week 52 by age at the Screening visit.

		To update the ANCOVA analysis for biceps muscle biopsies by removing Baseline factor as the values at Baseline are expected to be around 0 and exhibit extremely low variability	Sections 6.2.1.1, 6.2.12, Appendix 1 Removed text “Baseline (continuous variable)” from the ANCOVA model
		To evaluate actigraphy endpoints based on statistical model and aid in the interpretation of the treatment effect	Section 5.4, 6.3.2, Appendix 1 Added clarification that mean will be calculated for visits with at least 4 compliant days Added MMRM analysis for all actigraphy endpoints Added 95 th percentile of cadence actigraphy endpoint for Screening age strata subgroup analysis
		To correct typographical errors in the subgroup analysis for number of skills endpoints	Section 6.4.1 Removed MMRM description for NSAA total score Added the description of Binomial with logit link function
		To clarify the analysis for AEs of interest	Section 6.7.1 Added summary analysis for AEs of interest using incidence of all-causality adverse event (by severity) and SAEs Updated the interval duration for AE of interest by both cluster terms and the component PTs.
		To update subgroup analysis redefining Baseline NSAA total score groups by using median instead of tertile, and delete the analysis reporting p value for strata by treatment interaction for Baseline NSAA total score strata and Region.	Section 6.5.3, Appendix 1 Changed the definition of Baseline NSAA total score subgroups from tertiles-based to median-based. Removed the analysis to report p value of Baseline NSAA total score by treatment interaction, and Region by treatment interaction

090177e1a0727983\Approved\Approved On: 16-Apr-2024 16:39 (GMT)

		To clarify the analyses for select laboratory parameter	Section 6.7.2 Updated the summaries for CK, GGT, platelets, and creatinine by using data without normalization Updated shift table category
		To clarify the analyses for vital signs and ECG	Section 6.7.3, 6.7.4, Appendix 2.1 Removed text “(excluding unscheduled and early termination visits)” Clarified the algorithm for handling multiple values observed within a window Updated visit window at Week 2, Day14
		To clarify age calculation for different scenarios	Across the SAP Clarified screening age and age at dosing will be presented as integer for the demographic summary, rounded to one decimal place for baseline characteristic summary and statistical model analysis.
		To align the immune assay name across documents	Sections 3.3.3, 6.3.7, Appendix 1, Appendix 2 Changed ELISpot to T cell response

2. INTRODUCTION

This statistical analysis plan (SAP) provides the detailed methodology for summary and statistical analyses of the data collected in Study C3391003. This SAP specifically covers the analyses to be performed for the primary analysis that is to occur when all participants have completed visits through Year 1 Week 52 (or withdrawn from the study prior to Year 1 Week 52). There will be 2 additional SAPs to address other planned and optional analyses:

- One SAP will cover the analyses for the Cohort 2 delayed treatment and long-term safety and efficacy analyses.
- One SAP will cover the analyses for the two potential interim analyses (IAs) (See [Section 7](#)).

This document may modify the plans outlined in the protocol; however, any major modifications of the primary endpoint definition or its analysis will also be reflected in a protocol amendment.

2.1. Study Objectives, Endpoints, and Estimands

Only the study objectives, endpoints and estimands for the Primary Analysis through Week 52 will be presented in this SAP. The objectives for the Cohort 2 delayed treatment and long-

term safety and efficacy parts of the study will be presented in an additional SAP, as noted above.

2.1.1. Efficacy Objectives, Estimands, and Endpoints

Objectives Primary:	Endpoints Primary:	Estimands Primary:

To demonstrate superior efficacy of treatment with fordadistrogene movaparvovec as compared to placebo based on change from Baseline in the North Star Ambulatory Assessment (NSAA).
	
Change from Baseline at Week 52 in the NSAA total score.
	
Population: Boys with a genetic diagnosis of Duchenne muscular dystrophy (DMD) who are ambulatory and age ≥ 4 to < 8 years;
 
Variable: Change from Baseline at Week 52 in the NSAA total score;
 
 • Intercurrent event(s) and missing data: The potential intercurrent events are death or loss of ambulation. The intercurrent events and missing data will be handled as described below: • Death or loss of ambulation: NSAA total score will be set to 0 for all scheduled study visits after death or loss of ambulation (if not done after LoA). • Discontinuation from study: missing data from visits after a participant discontinues from the study (with the exception of death) will not be explicitly imputed. • Missing data from a participant not able to perform the NSAA due to acute illness or injury considered to be transient, will be assumed to be missing at random and will not be imputed. 
Population-level summary: difference in mean changes from Baseline at Week 52 in the NSAA total score between fordadistrogene movaparvovec and placebo.

Secondary:	Secondary:	Secondary:

090177e1a0727983\Approved\Approved On: 16-Apr-2024 16:39 (GMT)

Objectives	Endpoints	Estimands
To quantify the mini-dystrophin expression level in the muscle of participants treated with fordadistrogene movaparovec.	Change from Baseline in percent normal mini-dystrophin expression level in biceps brachii muscle biopsies at Day 360 (Week 52) using a liquid chromatography mass spectrometry (LCMS) assay.	Population: Boys with a genetic diagnosis of DMD who are ambulatory and age ≥ 4 to < 8 years;
To characterize the distribution of mini-dystrophin expression in the muscle of participants treated with fordadistrogene movaparovec .	Change from Baseline in percent of muscle fibers expressing mini-dystrophin in biceps brachii muscle biopsies at Day 360 (Week 52) as assessed by immunofluorescence.	Variable: Each secondary endpoint;
To characterize the change in serum creatine kinase (CK) concentration in participants treated with fordadistrogene movaparovec as compared to placebo.	Change from Baseline at Week 52 in serum CK concentration.	• Intercurrent event(s) and missing data: The potential intercurrent events are death and loss of ambulation. The intercurrent events and missing data will be handled as described below:
To characterize the skills gained, based on the individual items of the NSAA, in participants treated with fordadistrogene movaparovec as compared to placebo.	Number of skills gained at Week 52 based on the individual items of the NSAA.	• Loss of ambulation or death: secondary endpoints related to NSAA scores for individual skills (i.e., 10 meter run/walk velocity, rise from floor velocity, number of skills gained, and number of skills either improved or maintained) will be set to 0 for all scheduled study visits after loss of ambulation or death (if not done after LoA).
To characterize the skills either improved or maintained, based on the individual items of the NSAA, in participants treated with fordadistrogene movaparovec as compared to placebo.	Number of skills either improved or maintained at Week 52 based on the individual items of the NSAA.	• Discontinuation from Study: missing data from visits after a participant discontinues from the study (with the exception of death) will not be explicitly imputed.
To characterize the 10-meter run/walk velocity in participants treated with fordadistrogene movaparovec as compared to placebo.	Change from Baseline at Week 52 in the 10 meter run/walk velocity.	• Missing data from a participant not being able to perform the NSAA due to acute illness or injury, will not be explicitly imputed.
To characterize the rise from floor velocity in participants treated with fordadistrogene movaparovec as compared to placebo.	Change from Baseline at Week 52 in the rise from floor velocity.	• For all other secondary endpoints (i.e., mini-dystrophin, CK concentration, PODCI), missing data will not be explicitly imputed regardless of the causes.
To characterize the functional health status in participants treated with fordadistrogene movaparovec as compared to placebo.	Change from Baseline at Week 52 in the Modified Pediatric Outcomes Data Collection Instrument (PODCI): Transfer and Basic Mobility Core Scale (Pediatric Parent).	
	Change from Baseline at Week 52 in the Modified PODCI: Sports and Physical Functioning Core Scale (Pediatric Parent).	Population-level summary: difference in means between fordadistrogene movaparovec and placebo for each secondary endpoint.

Objectives	Endpoints	Estimands
Tertiary/Exploratory:	Tertiary/Exploratory:	
To assess the systemic immune response (humoral and cellular) to dystrophin in participants treated with fordadistrogene movaparvovec	Immune response (anti-drug antibodies (ADA) to mini-dystrophin and enzyme-linked immune absorbent spot (ELISpot)) to mini-dystrophin through Year 1 Week 52.	N/A
To assess the systemic immune response (humoral and cellular) to the AAV9 capsid in participants treated with fordadistrogene movaparvovec	Immune response (ADA, ELISpot, and NAb) to AAV9 through Year 1 Week 52.	N/A
To characterize the change in ankle range of motion in participants treated with fordadistrogene movaparvovec as compared to placebo.	Change from Baseline at Week 52 in passive ankle range of motion (dorsiflexion).	N/A
To characterize real-life function in participants treated with fordadistrogene movaparvovec as compared to placebo.	Change from Baseline at Week 52 in real-life function parameters as assessed by actigraphy.	N/A
To tabulate loss of ambulation in participants treated with fordadistrogene movaparvovec compared to placebo.	Loss of ambulation through Week 52.	N/A
To characterize pulmonary function in participants treated with fordadistrogene movaparvovec as compared to placebo.	Change from Baseline at Week 52 in %pFVC.	N/A
To characterize health-related quality of life in participants treated with fordadistrogene movaparvovec as compared to placebo	Response to each of the 5 dimensions of the EQ-5D-Y proxy assessment at Week 52	N/A
	Change from Baseline at Week 52 on the EQ visual analog scale (VAS) proxy assessment.	N/A
To characterize caregiver health-related QoL in caregivers of participants treated with fordadistrogene movaparvovec as compared to placebo.	Response to each of the 5 dimensions of the EQ-5D-5L assessment at Week 52.	N/A
	Change from baseline at Week 52 in the EQ-5D-5L VAS assessment.	N/A
	Change from baseline at Week 52 in the EQ-5D-5L index score.	N/A
To evaluate viral vector shedding following a single administration of fordadistrogene movaparvovec.	Quantification of viral vector shedding kinetics of fordadistrogene movaparvovec in whole blood, saliva and urine.	N/A

2.2. Safety Objectives and Endpoints

Objectives	Endpoints
To characterize the safety of treatment with fordadistrogene movaparvovec as compared to placebo.	
Incidence, severity and causal relationship of treatment-emergent AEs (TEAEs) (adverse events [AEs] and serious adverse events [SAEs]) through Week 52.
 
Incidence of abnormal laboratory findings and magnitude of change through Week 52.
 
Abnormal and clinically relevant changes through Week 52 in:
 
 • Physical exam; • Neurologic exam;

Objectives	Endpoints
	
 • Weight; • Vital signs; • ECG; • Echocardiogram; • Cardiac MRI • Child Behavior Check List (CBCL).

2.2.1. Primary Estimand(s)

Primary Estimand: difference in mean change from Baseline at Week 52 in the NSAA total score between fordadistrogene movaparvovec and placebo

- Population: Boys with a genetic diagnosis of DMD who are ambulatory and age ≥ 4 to < 8 years;
- Variable: Change from Baseline at Week 52 in the NSAA total score;
- Intercurrent event(s) and missing data: The potential intercurrent events are death or loss of ambulation. The intercurrent events and missing data will be handled as described below:
 - Death or loss of ambulation: NSAA total score will be set to 0 for all scheduled study visits after death. For participants with LOA, if NSAA test is done post LOA (to confirm a LOA), the NSAA total score from that assessment will be used. A value of 0 will be assumed if NSAA test is NOT DONE post a LOA.
 - Discontinuation from study: missing data from visits after a participant discontinues from the study (with the exception of death) will not be explicitly imputed.
 - Missing data from a participant not able to perform the NSAA due to acute illness or injury considered to be transient, will be assumed to be missing at random and will not be imputed.
- Population-level summary: Difference in mean changes from Baseline at Week 52 in the NSAA total score between fordadistrogene movaparvovec and placebo.

2.2.2. Secondary Estimand(s)

- Population: Boys with a genetic diagnosis of DMD who are ambulatory and age ≥ 4 to < 8 years;
- Variable: Each secondary endpoint;

- Intercurrent event(s) and missing data: The potential intercurrent events are death and loss of ambulation. The intercurrent events and missing data will be handled as described below:
 - Loss of ambulation or death: secondary endpoints related to NSAA scores for individual skills (i.e., 10 meter run/walk velocity, rise from floor velocity, number of skills either improved or maintained, and number of skills gained) will be set to 0 for all scheduled study visits after death. For participants with LOA, if the NSAA test is done post LOA, then the individual items from that assessment would be used in analyzing the secondary endpoints. A value of 0 would be assumed for the 17 NSAA items and the 2 velocity assessments only if the NSAA test is NOT DONE post a LOA.
 - Discontinuation from Study: missing data from visits after a participant discontinues from the study (with the exception of death) will not be explicitly imputed.
 - Missing data from a participant not being able to perform the NSAA due to acute illness or injury, will not be explicitly imputed.
 - For all other secondary endpoints (i.e., mini-dystrophin, CK concentration, PODCI), missing data will not be explicitly imputed regardless of the causes.
- Population-level summary: difference in means between fordadistrogene movaparvovec and placebo for each secondary endpoint.

2.2.3. Additional Estimand(s)

None.

2.3. Study Design

This is a Phase 3, global, multi-center, randomized, double-blind, placebo-controlled study to assess the safety and efficacy of fordadistrogene movaparvovec gene therapy in approximately 99 ambulatory male participants (in the FAS; see [Section 4](#)), ages ≥ 4 to < 8 years, with a genetic diagnosis of DMD who are on a stable daily regimen of glucocorticoids.

Eligible participants will be randomized into Cohort 1 or Cohort 2 in a 2:1 fashion and stratified by their age at Screening (< 6 or ≥ 6 years old). Study enrollment will be managed to ensure that no more than 55% of dosed participants are in either of the Screening age stratum. Enrollment will be assessed periodically, and if an imbalance is noted, enrollment of the overrepresented stratum may be paused until a more balanced distribution is achieved. In the context of this study, treatment will consist of two single intravenous infusions, one of fordadistrogene movaparvovec and one of placebo, with the timing and sequence as described below:

- Cohort 1 (approximately 66 participants): will receive a single dose of fordadistrogene movaparvovec on Day 1 (Visit 3) and a single dose of placebo at Day

DMB02-GSOP-RF02 4.0 Statistical Analysis Plan Template 01-Nov-2018

PFIZER CONFIDENTIAL

Page 14

TMF Doc ID: 98.03

390 (Visit 20). They will be followed for 5 years after the administration of the single dose of fordadistrogene movaparvovec. Total time on study will be approximately 5 years.

- Cohort 2 (approximately 33 participants): will receive a single dose of placebo on Day 1 (Visit 3) and a single dose of fordadistrogene movaparvovec at Day 390 (Visit 20), if they remain eligible. They will be followed for 5 years after the administration of the single dose of fordadistrogene movaparvovec. Total time on study will be approximately 6 years.

Figure 1. Study Schema

2.3.1. Sample Size Determination

The sample size of 99 participants in the FAS (see Section 4) is based on the primary efficacy endpoint of change from Baseline at Week 52 in the NSAA total score. The above sample size (assuming 3 participants will drop out of the study prior to Week 52) will provide 98% power to detect a treatment difference (fordadistrogene movaparvovec minus placebo) of 3.0. These calculations are based on $\alpha=0.05$ (two-sided), a 3-look group-sequential design with a gamma family (-1) spending function to determine the efficacy boundary, a gamma family (-4) spending function for the non-binding futility boundary, a common standard deviation of 3.5, and using the normal approximation of the test statistic for the comparison between two means.

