5. GENERAL METHODOLOGY AND CONVENTIONS

The primary analysis will occur after at least 90 FAS participants complete Day 360 (Visit 19) or discontinued from the study prior to Week 52 if they had received Year 1 IP at least

one year prior to the data cutoff. There are 2 options for IAs, both of which are designed to provide data to support an earlier regulatory submission for BLA/MAA as described in [Section 7](#).

As a general rule, all efficacy analyses including the primary endpoint, secondary endpoints, and other endpoints will be conducted based on all FAS participants regardless of adherence to background or protocol mandated glucocorticoid regimens during the first 52 weeks after study drug infusion, unless specified otherwise.

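### The SAP gives two triggers for the primary analysis, treats boys still in follow-up at the earlier one as dropouts in Sensitivity Analysis #1, and states a power about one point too high for its three-look design

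*SAP*

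**What the plan says.** **Timing.** Section 2 of the SAP refers to the "primary analysis that is to occur when all participants have completed visits through Year 1 Week 52", with those withdrawn before then also counted as done. Section 5 says: "The primary analysis will occur after at least 90 FAS participants complete Day 360 (Visit 19"), and also counts boys who discontinued before Week 52, provided they were dosed at least one year before the data cutoff. Section 4 footnote a repeats the 90-participant rule and attributes it to the definition in protocol amendment 15. The version history shows that the Section 5 text was added in version 9. Both rules stand in the current text.

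**Missing data.** The main MMRM imputes nothing explicitly and relies on MAR. Section 5.3 and Sensitivity Analysis #1 (Section 6.1.1.2) impute missing NSAA data by copy increments in reference. Placebo boys are imputed under MAR. Boys on fordadistrogene movaparvovec carry their last value forward with placebo-like changes, and Section 5.3 justifies this by progression after dropping out. Neither section mentions boys who are still in follow-up at the cutoff.

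**Power.** Section 2.3.1 starts from "The sample size of 99 participants in the FAS (see Section 4"). The stated result is that this number "will provide 98% power to detect a treatment difference (fordadistrogene movaparvovec minus placebo) of 3.0". The dropout allowance behind it is worded as "assuming 3 participants will drop out of the study prior to Week 52", and the design basis is given as follows: "These calculations are based on $\alpha=0.05$ (two-sided), a 3-look group-sequential design". Efficacy spending is gamma(-1), non-binding futility spending is gamma(-4), and the calculation assumes "a common standard deviation of 3.5, and using the normal approximation of the test statistic for the comparison between two means". Section 7 makes both interim analyses optional, at about 30 and about 60 completers.

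**The concern.** The two timing rules give different primary datasets. Under Section 2, every missing Week 52 score comes from a boy who left the study or missed the assessment. Under Section 5, some can be missing only because the boy was dosed late. Lateness of dosing is not a sign of disease progression, so the reason given for placebo-like increments does not apply to these boys. Because the text does not separate the two groups, a programmer following it would treat treated boys still in follow-up as dropouts. If the treatment works, that pulls the Sensitivity Analysis #1 estimate toward no difference for a reason unrelated to dropout, and the analysis no longer tests what it was written to test.

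The power statement is a lesser matter. It says that it includes three looks, yet the figure is that of a single-look test, and it was not supplemented when the 90-participant trigger came in.

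**Working it through.** **1. The two cutoffs**

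- Planned FAS: 99 (Section 2.3.1). Minimum at the Section 5 trigger: 90.
- Boys who may not yet have reached Week 52: 99 − 90 = 9, or 9/99 = 9.1% of the FAS. Any boys among the 90 who discontinued are additional.
- Section 2.3.1 plans for 3 dropouts, so this group could be up to 9/3 = 3 times as large as the planned dropout.
- "Eligible participants will be randomized into Cohort 1 or Cohort 2 in a 2:1 fashion" (Section 2.3). If the 9 split in that ratio, which is an assumption, about 6 are on fordadistrogene movaparvovec and would receive placebo increments in Sensitivity Analysis #1.

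**2. The plan's 98%**

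Inputs: difference 3.0, SD 3.5, two-sided alpha 0.05, normal approximation (all Section 2.3.1), and 2:1 allocation (Section 2.3).

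Drift = 3.0 / [3.5 × √(1/n₁ + 1/n₂)]; single-look power = Φ(drift − 1.960).

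- 66 vs 33: drift = 3.0/0.7462 = 4.020; Φ(2.060) = 0.9803.
- 64 vs 32 (3 dropouts): drift = 3.0/0.7578 = 3.959; Φ(1.999) = 0.9772.
- 60 vs 30: drift = 3.0/0.7826 = 3.833; Φ(1.873) = 0.9695.

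The first two both round to 98%.

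**3. The three-look design as stated**

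Gamma(-1) spending of the upper-tail 0.025: α(t) = 0.025 × (eᵗ − 1)/(e − 1).

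For looks at 30, 60 and 96 completers, t = 0.3125, 0.625 and 1. Cumulative alpha is 0.00534, 0.01263 and 0.025. Solving recursively gives bounds of 2.553, 2.365 and 2.110 (final two-sided p = 0.0349).

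Power is the summed probability of first crossing at each look, with mean drift × √tₖ and correlation √(tⱼ/tₖ) between looks. As a hand check, the final look alone gives Φ(3.959 − 2.110) = 0.968. Crossings at the earlier looks bring the total to 0.9705.

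| Week 52 completers | Single look | Three looks, futility ignored | Three looks, futility obeyed |
|---|---|---|---|
| 99 (looks 30/60/99) | 0.9803 | 0.9745 | 0.9726 |
| 96 (looks 30/60/96) | 0.9772 | 0.9705 | 0.9683 |
| 90 (looks 30/60/90) | 0.9695 | 0.9606 | 0.9577 |

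Equal spacing changes little: 0.9740 for 99 completers and 0.9701 for 96. No three-look row rounds to 98%, even with no dropout.

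**The case against.** On timing, the 90-participant rule is the more specific one, appears twice and is tied to the protocol amendment, while Section 2 is introductory. The operative trigger can therefore be guessed. That is fair and makes the repair easy, but the contradiction remains in current text. It also does not settle how boys still in follow-up enter Sensitivity Analysis #1.

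On power, the effect and SD are planning values, and a one-point gap near 97% changes no design decision. Both interims are optional, and without them the test is at 1.96 with 97.7% power for 96 completers. This stands, and it is why the power point is minor. It does not rescue the sentence, which says that it is computed for three looks.

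Three stronger readings are tempting but unsupported:

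- A reader might infer that the 98% ignores the 3 dropouts and comes only from 99 completers with no interim. But 96 completers with a single look give 97.7%, which also rounds to 98%. The arithmetic shows that the looks are not reflected; it does not show how the figure was obtained.
- A reader might infer that the Type II error is understated by half. That compares the 98% with a 90-participant cutoff for which Section 2.3.1 claims nothing. Ninety is also a minimum. For the design as stated, the comparison is about 3% against 2%.
- A reader might infer that the trial is underpowered. It is not: the lowest value in the table is 95.8%.

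**Conclusion.** The timing contradiction holds and is the main point. Up to 9 of 99 boys could be short of Week 52 at the Section 5 cutoff. This assumes that the FAS reaches its planned 99 and that the cut is made at the minimum of 90; a later cut shrinks the group. As written, the treated boys among them would be imputed as dropouts in Sensitivity Analysis #1.

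The stated power is about one point too high for the design it describes: about 97% (0.9705) with 96 completers and both looks. At exactly 90 completers it is about 96% with both looks and about 97% with none. These figures assume 2:1 allocation at every look, information proportional to Week 52 completers, and no credit for partial data in the MMRM. If some of the 90 have discontinued, completers are fewer and power is slightly lower. Partial data from boys still in follow-up work the other way.

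**What to change.** 1. In Section 2, replace the all-participants condition with the trigger in Section 5 and Section 4 footnote a.
2. In Sections 5.3 and 6.1.1.2, define FAS boys who are still in the study but not yet at Week 52 at the data cutoff as administratively incomplete. State that they are imputed under MAR in both arms, and reserve copy increments in reference for boys on fordadistrogene movaparvovec whose data are missing for other reasons, such as discontinuation. Fix the classification before unblinding.
3. In Section 2.3.1, restate the power as about 97% for 96 Week 52 completers with looks at 30, 60 and 96 (97.7% if no interim is run). Add that at the 90-participant minimum it is about 96% with both looks and about 97% with none.

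The cost is SAP wording and one derived flag for administrative incompleteness. Sample size, alpha spending and the primary model do not change. The stated power becomes slightly less favourable.
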